5.4.4. Safety Endpoints

Safety endpoints consist of the incidences of treatment-emergent adverse events (TEAEs), serious adverse events (SAEs) and discontinuations due to adverse events (AEs), vital signs (blood pressure, pulse, and body temperature), weight, suicidal ideation and behaviors assessed

by solicited questioning using the Columbia-Suicide Severity Rating Scale (C-SSRS), electrocardiograms (ECGs), laboratory measures (chemistry, hematology and urinalysis).

5.4.5. Immunogenicity Endpoints

Immunogenicity endpoints consist of the incidences of Anti-LY2951742 Antibody (hereafter Anti-Drug Antibody [ADA]) in all trial participants at baseline, including placebos (pre-existing ADAs), and in all trial participants at postbaseline (treatment-emergent ADAs). An additional endpoint is the incidence of Neutralizing ADA (NAb) present in those trial participants with ADAs.

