8.8.1. Samples for Immunogenicity Research

Where local regulations and ERBs allow, blood samples for immunogenicity testing will be collected to determine antibody production against LY2951742 as specified in the Schedule of Activities (Appendix 2). Immunogenicity will be assessed by a validated assay designed to detect anti-drug antibodies in the presence of the investigational product. Antibodies may be further characterized and/or evaluated for their ability to neutralize the activity of LY2951742.

Samples will be retained for a maximum of 15 years after the last patient visit for the study, or for a shorter period if regulations and ERBs impose shorter time limits, at a facility selected by the sponsor. The duration allows the sponsor to respond to future regulatory requests related to LY2951742.

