5.5.1.4. Analysis Populations

There were 4 analysis populations defined:

Intent-to-Treat (ITT) Population: All patients who are randomized and receive at least 1 dose of study drug.

Safety Population: This population is the same as the ITT population defined above.

Open-label treatment population: All patients who enter the open-label treatment phase (Study Period IV) as indicated by receiving any injections starting from V isit 7. Patients in the open-label treatment population will be analyzed as a single group as they start with the same dose in the study period. Analyses for open-label phase only will be based on open-label treatment population.

Post-treatment Population: All patients who enter the post-treatment phase (Study Period V) as indicated by entering any post-treatment visit (telephone or office visit). Analyses for post-treatment phase only (that is, excluding earlier study periods) will be based on post-treatment population.

Unless otherwise stated, all analyses will be analyzed according to the ITT principle on the ITT population. That is, patients will be analyzed according to the treatment they were randomized to, regardless of whether they actually received a different treatment.

Safety analyses (Section 5.5.1.2) and analyses for disposition and exposure will be conducted based on the modal treatment group patients have received (Placebo, LY120mg, or LY240mg) during the double-blind Study Period from the first to last injections at Visit 3 through Visit 6. For determining modal dose, do not consider the loading dose visit for subjects assigned to an LY120mg treatment group; do consider it for subjects assigned to the Placebo and LY240mg treatment groups. If there are 2 or more modes, then add the loading dose visit and recalculate the mode, if any. If a tie still remains, the highest LY dose of the modes will be used.

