5.5.1.5. Baseline and Postbaseline Definition

Table CGAI.5.4 describes the rules for determining the patient population and baseline and postbaseline observations for each study phase and type of analysis. When "last of Visit x-x" is used in the table, the last nonmissing observation obtained in the visit interval will be used.

Table CGAI.5.4. Patient Population with Baseline and Postbaseline Definitions by Study Period and Type of Analysis

Study Period / Analysis	Patient Population	Baseline Observation	Postbaseline Observation(s)
Study Period III			
Efficacy analyses (Repeated Measures) or average of observed monthly values	ITT Population with a baseline and at least 1 postbaseline observation	Visit 3	All scheduled visits 3 < Visits ≤7
Efficacy analyses at LOCF endpoint		Visit 3	Last of Visit 3.01-7
Quality of Life analyses (Repeated Measures)		Visit 3	All scheduled visits 3 < Visits ≤7
Quality of Life analyses at LOCF endpoint or for average of observed monthly values		Visit 3	Last of Visit 3.01-7
TEAEs	Safety Population	All Visits 1–3	All Visits 3.01–7
Serious Adverse Events, Discontinuations due to Adverse Events	Safety Population	NA	All Visits 3.01–7
C-SSRS categorical analyses	Patients with a baseline and at least 1 postbaseline C-SSRS assessment	Recent History: Visits 1–3 excluding lifetime ^a All Prior History: Visits 1–3 including lifetime ^a	All Visits 3.01–7
Treatment-emergent abnormal laboratory values	Safety Population with normal laboratory values at all nonmissing baseline visits (with respect to direction being analyzed) and who have at least 1 postbaseline observation	Low: Minimum from Visits 1–3 High: Maximum from Visits 1–3 Abnormal: All Visits 1–3	Low: Minimum from Visits 3.01–7 High: Maximum from Visits 3.01–7 Abnormal: All Visits 1–3
Treatment-emergent immunogenicity	Safety Population	Visit 3	All Visits 3.01–7
Treatment-emergent changes in temperature and weight	Safety Population with a baseline and at least 1 postbaseline observation	Low: Minimum from Visits 1–3 High: Maximum from Visits 1–3	Low: Minimum from Visits 3.01–7 High: Maximum from Visits 3.01–7
Treatment-emergent changes in blood pressures, pulse, and ECGs	Safety Population with a baseline and at least 1 postbaseline observation	Low: Last non-missing from Visits 1–3 High: Last non-missing from Visits 1–3	Low: Minimum from Visits 3.01–7 High: Maximum from Visits 3.01–7

Patient Population with Baseline and Postbaseline Definitions by Study Period and Type of Analysis

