Study Period / Analysis	Patient Population	Baseline Observation	Postbaseline Observation(s)
Study Period III	•	.	
Continuous safety analyses (Repeated Measures)	Safety Population with a baseline and at least 1 postbaseline observation	Last of Visits 1–3	All scheduled visits 3 < Visits ≤7
Continuous safety analyses – change from baseline to LOCF endpoint (ANCOVA)	Safety Population with a baseline and at least 1 postbaseline observation	Last of Visits 1–3	Last of Visits 3.01–7
Study Period IV			
TEAEs	Open Label treatment Population	All Visits 1-7	All Visits 7.01–16
Serious Adverse Events, Discontinuations due to Adverse Events	Open Label treatment Population	NA	All Visits 7.01–16
Treatment-emergent abnormal laboratory values	Open Label treatment Population and Patients with normal laboratory values at all nonmissing baseline visits (with respect to direction being analyzed) and who have at least 1 postbaseline observation	Low: Minimum from Visits 1–7 High: Maximum from Visits 1–7 Abnormal: All Visits 1–7	Low: Minimum from Visits 7.01-16 High: Maximum from Visits 7.01-16 Abnormal: All Visits 7.01-16
C-SSRS categorical analyses	Open Label treatment Population and Patients with a baseline and at least 1 postbaseline C-SSRS assessment	Recent History: All Visits 1–7 excluding lifetime ^a All Prior History: Visits 1 – 7 including lifetime ^a	All Visits 7.01–16
Treatment-emergent immunogenicity	Open Label treatment Population	Visit 3	All Visits 7.01–16
Treatment-emergent changes in temperature and weight	Open Label treatment Population and Patients with a baseline and at least 1 postbaseline observation	Low: Minimum from Visits 1–7 High: Maximum from Visits 1–7	Low: Minimum from Visits 7.01–16 High: Maximum from Visits 7.01–16
Treatment-emergent changes in blood pressures, pulse, and ECGs	Open Label treatment Population and Patients with a baseline and at least 1 postbaseline observation	Low: last non-missing from Visits 1–7 High: last non-missing value from Visits 1–7	Low: Minimum from Visits 7.01–16 High: Maximum from Visits 7.01–16

Patient Population with Baseline and Post-baseline Definitions by Study Period and Type of Analysis

			Postbaseline
Study Period / Analysis	Patient Population	Baseline Observation	Observation(s)
Study Period V			
TEAEs	Post-treatment Population	All Visits 1- 16	All Visits 16.01–18
Serious Adverse Events, Discontinuations due to Adverse Events	Post-treatment Population	NA	All Visits 16.01–18

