Post-treatment-emergent abnormal laboratory values	Post-treatment Population and Patients with normal laboratory values at all nonmissing baseline visits (with respect to direction being analyzed) and who have at least 1 postbaseline observation	All Visits 1- 16	All Visits 16.01–18
C-SSRS categorical analyses	Post-treatment Population and Patients with a baseline and at least 1 postbaseline C-SSRS assessment	Recent History: All Visits 1–16 excluding lifetime ^a All Prior History: Visits 1 – 16 including lifetime ^a	All Visits 16.01–18
Treatment-emergent immunogenicity	Post-treatment Population	Visit 3	All Visits 16.01–18
Post-treatment-emergent changes in temperature and weight	Post-treatment Population and Patients with a baseline and at least 1 postbaseline observation	Low: Minimum from Visits 1–16 High: Maximum from Visits 1–16	Low: minimum from Visits 16.01–18 High: maximum from Visits 16.01–18
Post-treatment-emergent changes in blood pressures, pulse, and ECGs	Post-treatment Population and Patients with a baseline and at least 1 postbaseline observation	Low: last non-missing from Visits 1–16 High: last non-missing from Visits 1–16	Low: minimum from Visits 16.01–18 High: maximum from Visits 16.01–18

Patient Population with Baseline and Post-baseline Definitions by Study Period and Type of Analysis

Study Periods III / IV Combined		-	
Efficacy analyses	ITT Population with a baseline and at least 1 postbaseline observation	Visit 3	All scheduled visits 3 < Visits ≤16
Quality of Life analyses	ITT Population with a baseline and at least 1 postbaseline observation	Visit 3	All scheduled visits 3 < Visits ≤16
Treatment-emergent immunogenicity	Safety Population	Visit 3	All Visits 3.01–16
Continuous safety analyses (Repeated Measures) Study Periods III/ IV/V Combined	Safety Population with a baseline and at least 1 postbaseline observation	Visit 3	All scheduled visits 3 < Visits ≤16
Efficacy analyses	ITT Population with a baseline and at least 1 postbaseline observation	Visit 3	All scheduled visits 3 < Visits ≤18
Quality of Life analyses	ITT Population with a baseline and at least 1 postbaseline observation	Visit 3	All scheduled visits 3 < Visits ≤18
Continuous safety analyses (Repeated Measures)	Safety Population with a baseline and at least 1 postbaseline observation	Visit 3	All scheduled visits 3 < Visits ≤18
Treatment-emergent immunogenicity	Safety Population	Visit 3	All Visits 3.01–18

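### The treatment-emergent ADA rows of SAP Table CGAI.5.4 require no ADA result, so patients who cannot be cases stay in the denominator

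*SAP*

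**What the plan says.** SAP 5.4.5 describes the endpoint as the incidence of ADA "in all trial participants at postbaseline (treatment-emergent ADAs").

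Table CGAI.5.4 in SAP 5.5.1.5 fixes the patient population for each analysis. Its immunogenicity entries for the separate study periods read:

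- Study Period (SP) III: "Treatment-emergent immunogenicity Safety Population Visit 3"
- SP IV: "Treatment-emergent immunogenicity Open Label treatment Population"
- SP V: "Treatment-emergent immunogenicity Post-treatment Population"

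The combined SP III/IV and SP III/IV/V rows also use the Safety Population. Under SAP 5.5.1.4 that is the ITT population: everyone randomized who received at least one dose. No sample is needed to belong to it. The Post-treatment Population is entered by any post-treatment contact, "as indicated by entering any post-treatment visit (telephone or office visit").

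Other measured variables in the same table are handled differently. The SP III C-SSRS row is limited to "Patients with a baseline and at least 1 postbaseline C-SSRS assessment". The temperature, weight, blood pressure, pulse and ECG rows ask for a baseline and at least one postbaseline observation. The laboratory rows ask for normal baseline values and at least one postbaseline observation.

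SAP 5.5.12.1.6 defines treatment-emergent ADA in two ways. One is a negative baseline followed by a positive result with a titer of at least 20. The other is a positive baseline followed by at least a 4-fold rise in titer. The section refers to Table CGAI.5.4 for baseline and postbaseline definitions and says nothing about missing samples. Protocol 8.8.1 makes sampling conditional: "Where local regulations and ERBs allow, blood samples for immunogenicity testing will be collected".

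**The concern.** ADA status is an assay result. The immunogenicity rows nevertheless follow the pattern of the adverse event rows, where a treated-patient denominator is suitable because no sample is needed for an event to be recorded. Here a patient lacking either result adds to the denominator and cannot add to the numerator, which has the same effect on the rate as calling that patient negative.

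Immunogenicity incidence is a prominent safety result for a monoclonal antibody, and any such bias runs downward. The gap would also be hard to see afterwards. The important protocol deviations in SAP Section 7 list missing C-SSRS, vital sign, laboratory and ECG data but not missing ADA samples. The ADA listings planned in 5.5.12.1.6 cover patients with ADA detected, not patients without a result.

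**Working it through.** **Plan's own figure.** There is none to reproduce. The documents state no expected ADA incidence and no missing-sample rate.

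**Step 1: numerator.** Both definitions in SAP 5.5.12.1.6 (treatment-induced and treatment-boosted) need an observed baseline and an observed postbaseline result. Only patients with both can be cases.

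**Step 2: denominator.** All five immunogenicity rows of Table CGAI.5.4 (SP III, IV, V, III/IV, III/IV/V) name a whole population with no data condition.

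**Step 3: identity.** Let x be the cases, n the patients with both results, N everyone in the named population, and u = 1 - n/N. Then

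x/N = (x/n) × (n/N) = evaluable incidence × (1 - u).

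The relative understatement is exactly u.

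**Step 4: numbers.** Both inputs are assumed, so a range is shown.

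| Evaluable incidence | u = 2% | u = 10% | u = 15% | u = 20% |
|---|---|---|---|---|
| 5% | 4.90% | 4.50% | 4.25% | 4.00% |
| 8% | 7.84% | 7.20% | 6.80% | 6.40% |
| 10% | 9.80% | 9.00% | 8.50% | 8.00% |

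As a check in counts, SAP 5.2 plans 285 + 285 = 570 patients on LY2951742. With u = 10%, n = 570 × 0.90 = 513. At 5%, cases = 25.65, and 25.65/570 = 4.50%.

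**Step 5: how large u might be.**

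- *SP III.* The Protocol's Schedule of Activities takes ADA samples at Visits 3, 4, 5, 6 and 7 and at early termination. Visit 4 is about day 14. A patient with a baseline sample is unevaluable only if they leave before about day 14 and also miss the termination sample, or miss every later sample. The 15% discontinuation rate in SAP 5.2 is therefore a loose reference point, not an estimate of u. Patients with no sample because of local rules would add to u; the documents do not say whether there are any.
- *Interim Analysis #2.* SAP 5.8.1.2 runs the ADA analyses on all available data, including SP IV and SP V, at a point when only SP III need be complete. The Visit 7 sample is drawn before the first open-label dose and the next is at Visit 8, targeted 30 days later. A patient dosed at Visit 7 shortly before the data cut is in the Open-Label Population with no result in that row's window (Visits 7.01–16). If the patient came from placebo, they are also LY-treated with no sample taken on LY2951742. Patients randomized to LY2951742 already have SP III samples, so the planned rate during LY treatment is affected mainly through those former placebo patients. Their number at the cut is not given.

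**The case against.** The strongest reply is that no sentence says a missing sample counts as negative or fixes the printed denominator. A programmer could reasonably set ADA status to missing. Protocol 9.2 requires a baseline and a postbaseline measurement when change from baseline is assessed. Part of this stands: the effect follows from combining the population column with the case definition, and is not stated outright. It does not dispose of the point. Protocol 9.2 does not expressly cover treatment-emergent ADA, the SAP states that it supersedes the protocol's statistical plans, and the SAP writes a data condition into neighbouring rows but not into these.

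A reader might infer more than the documents support:

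- *That 5.4.5 itself prescribes the denominator.* It only describes the endpoint. The point rests on Table CGAI.5.4 read with 5.5.12.1.6.
- *That the rate during LY treatment and the rate during LY treatment plus post-treatment are not comparable.* Both concern LY-treated patients, and the second window contains the first. Anyone evaluable in the first is evaluable in the second, so u cannot be larger there.
- *That SP V drives the problem.* SP V sampling is indeed sparse (Visit 18 or early termination), but 5.5.12.1.6 requests no stand-alone SP V incidence.
- *That the bias differs by arm.* The only planned between-group comparison is in SP III, where sampling is dense. Randomization is stratified by country, so a country without sampling would affect the arms about equally.

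**Conclusion.** The point holds as a specification fault. Taken literally, the immunogenicity rows give an incidence equal to the evaluable incidence times (1 - u), which is too low whenever any patient lacks a baseline or a postbaseline result. The identity is exact; its size is not known, because neither u nor the incidence is in the documents.

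In SP III the effect is probably small, of the order of 8% becoming 7.8% if u is 2%. It could be larger in the open-label data at Interim Analysis #2, depending on how many patients started open-label drug shortly before the cut. The conclusion assumes that the table is programmed as written. It does not extend to a difference between arms, to non-comparable LY-treated rates, or to the efficacy results.

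**What to change.** In every immunogenicity row of Table CGAI.5.4, and in 5.5.12.1.6, define an ADA-evaluable population: patients with a non-missing baseline ADA result and at least one non-missing postbaseline ADA result in the analysis window. Use it as the denominator for treatment-emergent ADA and for the combined treatment-emergent ADA and NAb-positive incidence. Report the number not evaluable by treatment group beside each rate.

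The cost is wording in a few cells and one extra line per table, with a slightly smaller denominator. The change does not make ascertainment complete. A patient with a single day-14 sample counts as evaluable although later seroconversion would be missed, and a patient with no baseline result is excluded even if a later titer is high. Showing the number not evaluable makes the excluded patients visible; it does not show how completely evaluable patients were sampled.

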5.4.7. Pharmacokinetic Assessment

Pharmacokinetic assessment will be summarized in the pharmacokinetic/pharmacodynamic (PK/PD) SAP.

5.5. Statistical Analyses

5.5.1. General Considerations

Treatment effects will be evaluated based on an overall 1-sided significance level of 0.025 for all efficacy and safety analyses. The 95% confidence intervals (CIs) for the difference in least-square means (LSMeans) between treatment groups will be provided.

Change from baseline of continuous variables with repeated measures will be analyzed using a mixed model repeated measures (MMRM) analysis. An MMRM analysis refers to a restricted maximum likelihood (REML)-based, mixed-effects repeated measures analysis using all the longitudinal observations at each postbaseline visit. Additionally, an analysis of variance (ANOVA) or an analysis of covariance (ANCOVA) model will also be used to analyze the change from baseline to average monthly measures during 3-month treatment phase (for measures with corresponding objectives evaluated over the 3-month treatment period) or to last-observation-carry-forward (LOCF) endpoint (for measures with corresponding objectives evaluated at Month 3). For other continuous variables, the change from baseline to LOCF endpoint will be analyzed using an ANOVA or ANCOVA model.

Unless otherwise specified, when ANOVA model or ANCOVA model is used to analyze a continuous efficacy variable, type III sum-of-squares for the LSMeans will be used for the statistical comparisons.

Binary variables with repeated measures will be analyzed in generalized linear mixed models (GLIMMIX) as pseudo-likelihood-based mixed effects repeated measures analysis.

For categorical efficacy variables without repeated measures, comparisons between treatment groups will be performed using logistic regressions. For other categorical variables without

repeated measures, comparisons between treatment groups will be performed using Cochran-Mantel-Haenszel (CMH) or Fisher's exact tests. Unless otherwise stated, CMH test will be controlled for baseline medication overuse (yes versus no) and concurrent prophylaxis use (yes versus no). Unless specified otherwise, Fisher's exact test will be used for comparisons of baseline measures (that is, baseline patient characteristics, previous therapy, etc.). The CMH test will be used for comparisons of postbaseline efficacy or safety measures when needed. The CMH test for postbaseline safety measures will be stratified by both baseline medication overuse and concurrent prophylaxis use, as baseline medication overuse and concomitant prophylaxis may have an impact on safety profiles.

For details of analysis methods, please refer to the following sub-sections.

Any change to the data analysis methods described in the protocol will require an amendment ONLY if it changes a principal feature of the protocol. Any other change to the data analysis methods described in the protocol, and the justification for making the changes, will be described in the SAP and/or in the clinical study report (CSR).

Additional exploratory analyses of the data will be conducted as deemed appropriate.

Statistical analysis of this study will be the responsibility of Eli Lilly and Company or designee. SAS® software will be used to perform most or all statistical analyses.

5.5.1.1. Adjustments for Covariates

The MMRM models will include the fixed, categorical effects of treatment, pooled country, month, baseline medication overuse (yes versus no), concurrent prophylaxis (yes versus no), and treatment-by-month interaction, as well as the continuous, fixed covariates of baseline value and baseline value-by-month interaction. The baseline value and baseline-by-month interaction are included to account for the differential influence over time that the baseline value has on the postbaseline values. Rules for pooling countries are defined in Section 5.5.1.3. Pooled country will be excluded in MMRM models for safety measures.

When an ANOVA model is used to analyze a continuous efficacy variable, the model will contain the main effects of treatment, baseline medication overuse (yes versus no), concurrent prophylaxis use (yes versus no) and pooled country. When an ANCOVA model is used to analyze a continuous efficacy variable, the model will contain the main effects of treatment, baseline medication overuse (yes versus no), concurrent prophylaxis use (yes versus no) and pooled country, and appropriate baseline value as a covariate. When an ANOVA or ANCOVA model is used to analyze a continuous safety variable, pooled country will be removed from the model.

The GLIMMIX models for the repeated binary outcomes will include the fixed, categorical effects of treatment, month, baseline medication overuse (yes versus no), concurrent prophylaxis (yes versus no), and treatment-by-month interaction, as well as the continuous, fixed covariate of baseline value. Pooled country and the baseline value-by-month interaction will be excluded from the model in order to increase the likelihood of convergence.

When a logistic regression is used to analyze a binary variable, the model will include the main effect of treatment, baseline medication overuse (yes versus no), concurrent prophylaxis use (yes versus no) and pooled country, and appropriate baseline value as a covariate. Pooled country may be excluded from the model in case of non-convergence.

